8.6.6 Demographic Data and Other Baseline Characteristics

Listings and descriptive summary statistics of demographic (age, height, weight and BMI) and baseline data will be presented.

8.6.7 Pharmacokinetics

The PK analysis will be carried out according to CRO's SOPs. PK data handling and analysis will be further detailed in a SAP.

The PK parameters for nicotine (baseline unadjusted and baseline adjusted [if applicable]) are presented in Table 5.

Parameter	Definition
C _{max}	Maximum observed concentration
T _{max}	Time of maximum observed concentration; if it occurs at more than one time point, T_{max} is defined as the first time point with this value
AUC _{0-6h}	Area under the concentration time curve from the time of product administration to T_{6h}

8.6.7.1 Pharmacokinetic Statistical Methodology

8.6.7.1.1 Descriptive Statistics

Individual raw PK concentration data and derived concentrations will be calculated with the build-in Phoenix[®] WinNonlin[®] platform and displayed with the same precision as received from the bioanalytical laboratory.

Descriptive statistics will be calculated for concentrations at each individual time point and for all PK parameters. Individual concentrations, actual sampling times, and PK parameters obtained from the Non-Compartmental Analyses (NCA) will be summarised per test product group using the following descriptive statistics: number of observations (N), minimum, arithmetic mean, geometric mean, median, maximum, standard deviation (SD), coefficient of variation (CV%).

8.6.7.1.2 Statistical Analysis

8.6.7.1.2.1 Study Product Comparisons

The study product comparisons of interest are presented in Table 6. There are seven primary comparisons for the primary PK parameters AUC_{0-6h} and C_{max} .

Table 6. Study Product Comparisons

Primary	Other				
Effect of nicotine strength (3 vs 2)	All MOPs vs Swedish snus (2-8 vs 1)				
Effect of alginate (4 vs 3)					
Effect of acid inclusion (3 vs 6; 3 vs 7; 2 vs 5)					
Effect of acid type (6 vs 7)					
Effect of sweet base (8 vs 6)					

Abbreviations: MOP=Modern oral product

Note: see Section 8.3.1 for product numbering

8.6.7.1.3 Primary Analysis

The geometric mean nicotine $AUC_{0.6h}$ and C_{max} between the study products will be compared using a mixed-effect ANOVA model with treatments, periods, sequences as fixed effects and subjects nested within sequences as random effects. Treatment comparisons will be conducted using the fitted model with adjusted significance level of 0.00714. Data will be analysed on the natural log (ln)-transformed scale.

The superiority hypothesis to be tested is:

H0: µ≤1 vs. H1: µ>1

where μ is the ratio of primary PK parameter (AUC_{0-6h} or C_{max}) between a pair of study products. Following the ln-transformation the interchangeable hypothesis will be:

H0: $\Delta \leq 0$ vs. H1: $\Delta > 0$

where Δ is the paired difference of primary PK parameter (AUC_{0-6h} or C_{max}) between pair of study products.

Both comparisons (AUC_{0-6h} and C_{max}) will need to be statistically significant at the one-sided Holm adjusted 0.05 level to show superiority for a primary comparison (3 vs 2, 4 vs 3, 3 vs 6, 3 vs 7, 2 vs 5, 6 vs 7 and 8 vs 6). For descriptive purposes, unadjusted p-values will be provided for other study product comparisons.

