8.6.8 Determination of sample size

8.6.8.1 Primary Analysis

Seven one-sided primary superiority comparisons (products 3 vs 2, 4 vs 3, 3 vs 6, 3 vs 7, 2 vs 5, 6 vs 7 and 8 vs 6; see Section 8.3.1 for product numbering) will be performed in this study which utilises an 8-product and 8-sequence Williams crossover design. A minimum of 32 subjects (4 subjects per sequence) will be needed to achieve a balanced design and a power of 0.848 with an alpha level of 0.00714. This will enable detecting a difference of 25% in the log scale with a correlation of 0.3 and an intrasubject CV of 0.3. A total of 36 subjects will thus be needed to be included, if an overall drop-out rate of 10% is assumed in the study.

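### The primary analysis gives two different significance rules for the seven primary comparisons, a fixed 0.00714 and one-sided Holm at 0.05, and does not say which governs

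*Protocol*

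**What the plan says.** Section 8.6.7.1.2 sets the family: "There are seven primary comparisons for the primary PK parameters" AUC0-6h and Cmax. Section 8.6.7.1.3 then describes the mixed model on the log scale and states: "Treatment comparisons will be conducted using the fitted model with adjusted significance level of 0.00714". After the hypotheses, the same section says that both parameters "will need to be statistically significant at the one-sided Holm adjusted 0.05 level to show superiority for a primary comparison", and lists all seven comparisons.

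Section 8.6.8.1 plans for "Seven one-sided primary superiority comparisons" and claims "a power of 0.848 with an alpha level of 0.00714" at 32 subjects. Section 8.6.4.4 requires a multiplicity adjustment and leaves its details to the SAP. Nowhere does the protocol say that 0.00714 is only the first Holm step, or only a planning value.

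**The concern.** A fixed 0.00714 and a Holm procedure at 0.05 are different decision rules. The fixed level holds every comparison to the same strict cut-off. Holm holds only the smallest p-value to it and relaxes the cut-off after each rejection. Section 8.6.7.1.3 applies both to the same seven comparisons, so an analyst who follows one sentence departs from the other. What is at stake is how many of the seven product contrasts may be declared superior.

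There is a related gap. Both parameters must be Holm-significant, but the section does not say whether Holm is run once on one p-value per comparison or separately for AUC0-6h and for Cmax with the results then combined. The two do not have the same error properties.

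**Working it through.** **1. Where 0.00714 comes from.** 0.05/7 = 0.00714, the Bonferroni level for seven comparisons. Counting both parameters would give 0.05/14 = 0.00357, which does not match.

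**2. The plan's own power.** Inputs from section 8.6.8.1: n = 32, a 25% difference read as a ratio of 1.25, CV 0.3, correlation 0.3, one-sided alpha 0.00714.
- Log-scale SD: sqrt(ln(1 + 0.3²)) = 0.2936
- Log-scale correlation: ln(1 + 0.3 × 0.09)/ln(1.09) = 0.309
- Standard error of a paired difference: 0.2936 × sqrt(2 × (1 − 0.309)/32) = 0.0610
- Noncentrality: ln(1.25)/0.0610 = 0.2231/0.0610 = 3.66
- Power from the noncentral t with 31 df: 0.848, as stated

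The 36 randomised also follows: 32/0.90 = 35.6, rounded up. The sample size was therefore built on the fixed level, for one parameter in one comparison.

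**3. The two rules side by side.** Holm compares the k-th smallest p-value with 0.05/(7 − k + 1) and stops at the first failure. The last column is the step 2 power at each Holm threshold.

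| Step k | Fixed | Holm | Power at Holm threshold |
|---|---|---|---|
| 1 | 0.00714 | 0.00714 | 0.848 |
| 2 | 0.00714 | 0.00833 | 0.863 |
| 3 | 0.00714 | 0.01000 | 0.879 |
| 4 | 0.00714 | 0.01250 | 0.897 |
| 5 | 0.00714 | 0.01667 | 0.918 |
| 6 | 0.00714 | 0.02500 | 0.943 |
| 7 | 0.00714 | 0.05000 | 0.973 |

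**4. Same data, different conclusions.** Take the larger of the AUC0-6h and Cmax p-values for each comparison.
- 0.001, 0.001, 0.002, 0.008, 0.010, 0.012, 0.020: three are below 0.00714, so the fixed rule gives three claims. Under Holm each value is below its own threshold (for example 0.008 < 0.01250 and 0.020 < 0.05), so all seven are claimed.
- 0.003, 0.008 and five at 0.3: one claim under the fixed rule, two under Holm (0.008 < 0.00833).

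**5. How often this would happen.** Simulation of the seven contrasts on eight product means: 100,000 trials, n = 32, 210 df, larger p-value per comparison, assumed AUC-Cmax correlation 0.5 to 0.8. The true effects are assumptions, since the protocol gives none per comparison. In the scenario with all seven real, the ratios are 2.0 for 3 vs 2, 1.25 for five comparisons, and 1.25² = 1.56 for 3 vs 7, which is the product of 3 vs 6 and 6 vs 7.

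| Scenario | Trials in which the rules disagree on at least one comparison |
|---|---|
| Only nicotine strength real (ratio 2.0) | 0.1% to 0.3% |
| Strength plus acid inclusion (1.25) real | about 17% |
| All seven real, protocol's correlation of 0.3 used | about 50% to 54% |
| All seven real, CV 0.3 taken as the residual | about 63% to 64% |

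With all seven effects real and the protocol's planning variance, power to win on both parameters at ratio 1.25 is about 0.80 to 0.83 under the fixed level and about 0.94 to 0.96 under Holm.

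**6. Running Holm separately per parameter.** Each run controls its own error at 0.05. If some comparisons are null only in AUC0-6h and the rest only in Cmax, a false claim can come from either run, so the two errors add. With independent runs the limit is 1 − 0.95² = 0.0975. Simulation (400,000 trials, independent statistics, overwhelming non-null effects) gives 0.095 to 0.097, against 0.048 to 0.049 for a single Holm run on the larger p-values. Under less extreme split-null assumptions, simulated values were 0.061 to 0.075 (typical non-null ratio 1.25) and 0.075 to 0.091. When the nulls coincide in both parameters, it is only 0.006 to 0.018.

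**The case against.** The best defence is that the Holm sentence is the only one that states a success criterion, while the 0.00714 sentence belongs to the description of the model. On that reading 0.00714 is Holm's starting level and the conservative planning alpha, and section 8.6.4.4 leaves the details to the SAP. The reading is sensible and is the one the fix adopts. But the text does not say it: section 8.6.7.1.3 attaches 0.00714 to the treatment comparisons from the fitted model, with no mention of ordering or steps. Deferring details does not reconcile two rules that the protocol itself states.

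The rest of the defence stands. Both rules control the family-wise error at one-sided 0.05 if fixed in advance. Holm rejects everything the fixed level rejects. The sample size uses the stricter level, so it needs no change. The high disagreement rates require all seven effects to be real.

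A reader might go further and infer that the plan nearly doubles its error rate. The documents do not support that: neither stated rule inflates the error, and the excess arises only if Holm is run separately per parameter and the nulls are split between two measures taken from the same concentration profile. Nor can it be inferred that the rule will be chosen after the p-values are seen. The SAP is not at hand and may settle it, and section 8.3.5 withholds the randomisation code until after database lock.

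**Conclusion.** The protocol contradicts itself on the decision threshold for its seven primary comparisons, and this should be corrected. The consequence is a possible difference in the number of superiority claims, always with Holm giving at least as many, and not a loss of validity under either stated rule.

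The size cannot be given as one figure. It runs from under 1% of trials to about 50% to 64%, depending on the true effects and on how the CV is read. A reader who takes CV 0.3 as the residual and ignores the stated correlation might infer a larger loss, with power at ratio 1.25 of 0.57 to 0.63 under the fixed level against 0.77 to 0.83 under Holm. Those figures do not rest on the variance that reproduces the protocol's 0.848.

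A family-wise error of about 0.08 to 0.10 is a worst case under the separate-runs reading. It is a reason to specify how the two parameters are combined, not a property of the plan as written.

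**What to change.** In section 8.6.7.1.3, replace the sentence that fixes 0.00714 and complete the Holm sentence so that one rule remains:
- for each of the seven primary comparisons, take p = max(p_AUC, p_Cmax);
- apply Holm once to these seven p-values at a one-sided family-wise level of 0.05;
- describe 0.00714 (0.05/7) only as Holm's first threshold and as the conservative alpha used for the sample size in section 8.6.8.1.

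The SAP should carry the same wording. The cost is two sentences, with no effect on the number of subjects, the conduct of the study or the data collected. It should be settled before database lock and release of the randomisation code.

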8.6.7.1.4 Secondary Analysis

Product satisfaction

Product satisfaction data will be listed by subject and summarised for each product using frequencies (n, %).

Residual nicotine in used pouches

Nicotine transfer levels will be listed by subject and summarised for each product using descriptive statistics.

The PK statistical analyses will be detailed in the SAP.

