5.1 Rationale for study design

This study was designed to assess nicotine uptake for modern oral products in comparison to traditional tobacco containing Swedish snus to understand product efficacy at delivering nicotine, provide safety data and inform product design. A crossover design was chosen to minimise variability and the number of subjects needed for evaluation. Subjects will be randomised to study product sequences to minimise assignment bias. By necessity, the subjects will not be fully blinded due to the different visual appearances between the snus product and the seven oral nicotine products. This is not anticipated to impact the outcome of the study endpoints. The bioanalytical laboratory will be blinded.

As the purpose of this study is to assess nicotine uptake for modern oral products in comparison to traditional snus, 8 smokeless nicotine pouch products will be used in this study. Smokeless pouch users or loose snus users as well as dual users (smokers or e-cigarette users and smokeless pouch or loose snus users) will be recruited.

To avoid any carry-over effect, a wash-out of 12 hours is planned between product administrations. Given the expected half-life of nicotine (about 2 hours), this wash-out period is judged to be sufficient.

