7.3 Secondary objectives and endpoints

The secondary objectives of this study are to evaluate product subjective measures of the different smokeless nicotine products and to determine the amount of residual nicotine in the used pouches.

Secondary endpoints are the scores on the product subjective measures questionnaires and the amount of residual nicotine in the used pouches.

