8.4.2 Clinical efficacy assessments

This is a pharmacokinetic study and the only assessment of clinical efficacy of the products is the subjects' subjective experience of each product as measured by Product Subjective Measures Questionnaires (Appendix 19.3).

Subjects will answer short questionnaires on their liking of the product and their overall intent to use the product again following the end of use of each study product (i.e., 60 ± 5 minutes) in periods 1 to 8.

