19.2 Clinical Laboratory Evaluations

19.3 Product Subjective Measures Questionnaires

Subject number: _____

Date of completion: ____ / ___ / 20____

Product: _____

Product Liking Questionnaire (PLQ)

At this moment, how much do you like the product?

0	1	2	3	4	5	6	7	8	9	10
Strongly					Neither					Strongly
dislike					like nor					like
					dislike					

Overall Intent to Use Again (OIUA) Questionnaire

Rate the degree to which you would like to use the product again.

0	1	2	3	4	5	6	7	8	9	10
Not at all										Very
										much

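### The 0-10 liking and intent-to-use-again scores are summarised only as frequencies per product, so the planned summary gives no within-subject product difference and no precision

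*Protocol*

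**What the plan says.** Section 7.3 sets the secondary objective, in part, as "to evaluate product subjective measures of the different smokeless nicotine products", and names the endpoint: "Secondary endpoints are the scores on the product subjective measures questionnaires and the amount of residual nicotine in the used pouches".

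Appendix 19.3 has two items, each scored from 0 to 10. One asks "At this moment, how much do you like the product"; the other says "Rate the degree to which you would like to use the product again". Under section 8.4.2 both are completed at the end of use of each product, in all eight periods: "Subjects will answer short questionnaires on their liking of the product and their overall intent to use the product again". The same section treats these ratings as the trial's sole measure of clinical efficacy.

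Section 8.6.7.1.4 then fixes how they are summarised: "Product satisfaction data will be listed by subject and summarised for each product using frequencies (n", with the percentage alongside. I read product satisfaction there as these two scores, since the protocol collects no other satisfaction measure. In the same section residual nicotine, the other secondary endpoint, gets descriptive statistics. The closing reference to the SAP in that section names the PK analyses only.

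**The concern.** Section 5.1 explains the design: "A crossover design was chosen to minimise variability and the number of subjects needed for evaluation". The benefit comes from comparing products within the same person. A separate frequency table per product does not use it, because the table does not record which subject's rating of one product goes with which rating of another.

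Counts by category also suit an 11-level numeric rating poorly at this sample size, and the protocol names no mean, median or difference beside them. At stake is how well the report can describe whether strength, alginate, acid or sweet base changes liking or intent to use again. These are product-design questions, and sections 5 and 5.1 say the study should inform product design.

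**Working it through.** **The plan's own figures.** The protocol states no power, SD, correlation or precision for the scores. Its one power figure, 0.848 in section 8.6.8.1, concerns the PK comparisons. It reproduces closely (0.843 by a paired t calculation with 31 degrees of freedom) and has no bearing here.

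**Inputs from the protocol.** 11 levels per item (0 to 10, Appendix 19.3); 8 products, each rated by every completer (section 8.4.2); 32 completers, 36 randomised (section 8.6.8.1).

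**Step 1: sparsity.** Cells per questionnaire = 11 × 8 = 88. Average subjects per level for one product = 32/11 = 2.9 (36/11 = 3.3 if nobody drops out). This is an average. Real scores will cluster, so some cells will be larger and others empty.

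**Step 2: what the tables cannot separate.** Take illustrative scores for two products in 32 subjects, then shuffle one product's scores across subjects. Both frequency tables, and the mean difference of 1.19, stay exactly the same.

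| Pairing | SD of differences | 95% CI half-width = t(0.975; 31) × SD/√32 |
|---|---|---|
| As generated | 0.74 | 0.27 |
| Shuffled | 3.33 | 1.20 |

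The precision of the difference changes more than fourfold (1.20/0.27 = 4.4) with no change in the planned summary. The scores are invented; only the logic carries over to the trial.

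**Step 3: what pairing is worth.** Let each score have SD s and let two ratings by the same subject have correlation ρ. Then:

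- variance of a paired mean difference = 2s²(1 − ρ)/n;
- variance when pairing is ignored = 2s²/n;
- ratio = 1 − ρ.

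Both s and ρ are my assumptions. 95% CI half-widths in scale points, n = 32 (t with 31 degrees of freedom when paired, 62 when pairing is ignored):

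| s | ρ = 0 | ρ = 0.3 | ρ = 0.5 | ρ = 0.7 | Pairing ignored |
|---|---|---|---|---|---|
| 2.0 | 1.02 | 0.85 | 0.72 | 0.56 | 1.00 |
| 2.5 | 1.27 | 1.07 | 0.90 | 0.70 | 1.25 |
| 3.0 | 1.53 | 1.28 | 1.08 | 0.84 | 1.50 |

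The variance falls by 30% at ρ = 0.3 and by 70% at ρ = 0.7. At ρ = 0 there is no gain.

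**The case against.** **The objective is only to evaluate.** This stands. Section 7.1 makes comparison an aim for PK parameters, and Table 6 is tied to AUC and Cmax. No hypothesis or power is stated for the scores. A reader might infer that a descriptive summary contradicts the secondary objective or that a formal test is owed. The protocol supports neither.

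**Frequency tables do show differences.** This also stands. If tabulated by level, they give each product's whole distribution, and a mean, median or SD can be derived from it. With complete data, the difference of two product means equals the mean paired difference. It would be wrong to say the tables cannot show how products differ. What is missing is the paired precision and an explicit estimate.

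**The data are also listed by subject.** True. A reader might infer that the pairing is thrown away, but it is lost from the summary and not from the report. A listing still leaves the reader to do the analysis.

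**The SAP may add more.** It may, and nothing in section 8.6.7.1.4 forbids it; section 8.6.4 also leaves details of the analysis and comparisons to the SAP. But the protocol names a specific method for these scores, and section 8.6.7.1.4 defers only the PK analyses. The named choice can therefore be judged as it stands. If the SAP already contains such estimates, the point is met.

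**More contrasts raise multiplicity.** Seven Table 6 pairs plus seven comparisons with snus, on two scales, make (7 + 7) × 2 = 28 estimates, and section 8.6.4.4 requires adjustment for multiple comparisons. This is a fair reason to report intervals without tests and to say so explicitly.

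**Conclusion.** The concern holds as a minor point. The only summary named for the scores is frequencies per product. With about 2.9 subjects per level on average it will be sparse, and it supplies no within-subject product difference and no precision, although each completer rates all 8 products.

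The size of the gain is uncertain. Pairing reduces the variance of a difference by about 30% to 70% at assumed correlations of 0.3 to 0.7, and by nothing at 0; the protocol gives no figure to narrow this. Even at a correlation of 0, an estimate with an interval would tell the reader more than the frequencies alone.

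Nothing here touches the primary analysis, its power or the sample size.

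**What to change.** In section 8.6.7.1.4, or in the SAP before database lock:

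- Keep the frequencies and the subject listing.
- Add mean, SD and median per product for each of the two scores.
- Fit the crossover model of section 8.6.7.1.3 (product, period and sequence fixed; subject within sequence random) to each score. Leave the scores untransformed, because a score of 0 has no logarithm.
- Report mean differences with 95% CIs for the seven Table 6 pairs and for each of products 2 to 8 versus snus.
- Label these descriptive, with no hypothesis tests or superiority claims, and state how this sits with the adjustment rule in section 8.6.4.4.

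The cost is modest extra output: two model fits and 28 estimates, with no new data, subjects or visits. The technical downside is that an 11-point score is treated as approximately continuous; the retained frequencies let a reader see where that is strained.

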8.6.8 Determination of sample size

8.6.8.1 Primary Analysis

Seven one-sided primary superiority comparisons (products 3 vs 2, 4 vs 3, 3 vs 6, 3 vs 7, 2 vs 5, 6 vs 7 and 8 vs 6; see Section 8.3.1 for product numbering) will be performed in this study which utilises an 8-product and 8-sequence Williams crossover design. A minimum of 32 subjects (4 subjects per sequence) will be needed to achieve a balanced design and a power of 0.848 with an alpha level of 0.00714. This will enable detecting a difference of 25% in the log scale with a correlation of 0.3 and an intrasubject CV of 0.3. A total of 36 subjects will thus be needed to be included, if an overall drop-out rate of 10% is assumed in the study.

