7.2 Primary endpoint(s)

The primary study endpoints are the PK parameters C_{max} and AUC_{0-6h} of nicotine.

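### The stated power of 0.848 is for one PK parameter, but a comparison succeeds only if both AUC0-6h and Cmax are significant; joint power at 0.00714 is about 0.75 to 0.80

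*Protocol*

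**What the plan says.** Section 7.2 of the protocol names two primary endpoints: "The primary study endpoints are the PK parameters C_{max} and AUC_{0-6h} of nicotine".

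Section 8.6.7.1.3 sets the level, "Treatment comparisons will be conducted using the fitted model with adjusted significance level of 0.00714", and then the success rule: the tests of AUC0-6h and Cmax "will need to be statistically significant at the one-sided Holm adjusted 0.05 level to show superiority for a primary comparison". A comparison therefore succeeds only when two tests succeed.

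Section 8.6.8.1 plans "Seven one-sided primary superiority comparisons". It gives the size as "A minimum of 32 subjects (4 subjects per sequence) will be needed to achieve a balanced design", together with "a power of 0.848 with an alpha level of 0.00714", for "detecting a difference of 25% in the log scale with a correlation of 0.3 and an intrasubject CV of 0.3". It states one effect, one CV, one correlation and one power. It names neither parameter, does not mention that both must be significant, and gives no correlation between AUC0-6h and Cmax.

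**The concern.** A reader of section 8.6.8.1 will take 0.848 as the chance that a true 25% difference is declared by the protocol's own criterion. If the figure covers one parameter only, that chance is overstated at the same level and sample size, even when every planning value is accepted.

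The practical consequence is the split result, with one parameter significant and the other not, which counts as a failure to show superiority. Without a joint figure, a reader cannot tell how often a real 25% effect would end that way, and may read a failed comparison (for alginate or acid type, say) as stronger evidence of no difference than it is. Only power is at stake: requiring both parameters does not inflate the type I error.

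**Working it through.** **Inputs from section 8.6.8.1.** n = 32 completers; one-sided level 0.00714 (= 0.05/7); difference 25%, taken as a ratio of 1.25, so ln 1.25 = 0.2231; CV 0.3; correlation 0.3.

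**Step 1: reproduce 0.848.** Treat it as a one-sided paired t-test of a mean ratio on lognormal data, for one parameter and one comparison.

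- Log-scale variance: ln(1 + 0.3²) = ln 1.09 = 0.08618.
- Log-scale correlation between products: ln(1 + 0.3 × 0.3²)/0.08618 = ln 1.027/0.08618 = 0.3092.
- SD of the paired log difference: √(2 × 0.08618 × (1 − 0.3092)) = 0.3451.
- Noncentrality: 0.2231/(0.3451/√32) = 3.658.
- Critical value of t on 31 df at one-sided 0.05/7: 2.596.
- Power from the noncentral t: 0.8482.

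This matches the stated figure to three decimals. Using 0.3 directly as the log-scale correlation gives 0.843, and a two-sided level gives 0.774. Reading 0.3 as the AUC-Cmax correlation in a two-parameter calculation gives 0.49 to 0.82, depending on how the 25% and the CV are converted, and never 0.848. So the 0.3 acts as the between-product correlation and 0.848 is a one-parameter power.

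**Step 2: power of the rule that both must be significant.** Simulate pairs of t statistics (10⁶ draws), each parameter with its own variance estimate on 31 df, both with noncentrality 3.658, and require both to exceed 2.596. The correlation of the paired AUC0-6h and Cmax differences is not in the protocol and is assumed over a range.

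| Assumed AUC-Cmax correlation | Joint power | Shortfall from 0.848 | Chance of a split result |
|---|---|---|---|
| 0.5 | 0.75 | 0.10 | 0.19 |
| 0.7 | 0.77 | 0.07 | 0.15 |
| 0.8 | 0.79 | 0.06 | 0.12 |
| 0.9 | 0.80 | 0.04 | 0.09 |

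The last two columns use unrounded joint powers (0.752, 0.773, 0.787, 0.805). The split probability is 2 × (0.848 − joint power). At correlation 0.8, for instance, it is 2 × (0.848 − 0.787) = 0.12, and the type II error rises from 15% to 21%.

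**Step 3: relax the equal-parameter assumption.** Keep n = 32, level 0.00714 and AUC-Cmax correlation 0.8.

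- Second parameter with CV 0.25: joint power 0.84. With CV 0.22: 0.847. With CV 0.20: 0.848.
- Equal CVs, but a true ratio of 1.35 on the second parameter: 0.847.

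**Step 4: allow for Holm.** With equal parameters and correlation 0.8, joint power is 0.79 at 0.05/7, 0.81 at 0.05/6, 0.83 at 0.05/5 and 0.85 at 0.05/4. Simulating the full step-down over AUC-Cmax correlations from 0 to 0.9 gives 0.71 to 0.81 when one comparison alone is truly 25%. When all seven true effects are at least 25%, it gives 0.90 to 0.96 for each comparison at 25%.

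**The case against.** The strongest reply is that 0.848 is arithmetically right for what it computes, and that the loss may be small. Both parameters come from the same concentration profile, so their correlation should be high. A correlation of 0 (joint power 0.72) is not realistic, and at 0.8 to 0.9 the shortfall is about 4 to 6 points. That stands and limits the size of the point, but the protocol states no correlation from which a reader could judge this.

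A reader might go further and infer that joint power must be below 0.848 unless the two parameters are perfectly correlated. The documents do not support that. It holds only at 0.00714 and only if effect and CV are the same for both parameters. Section 8.6.8.1 does not say which parameter its CV describes. If it describes the more variable one, step 3 shows that the loss almost vanishes, although at 0.00714 joint power still cannot exceed the power of the weaker parameter.

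Nor can one say that power is below 0.848 in every scenario under the stated rule. That rule is Holm-adjusted, and its level relaxes as other comparisons are rejected. The power sentence uses 0.00714, however, and does not assume that other comparisons succeed, so on the protocol's own planning basis the gap remains.

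A reader might also recompute with 0.3 as a residual within-subject CV and no correlation term, which would give lower powers. That drops an input the protocol states and raises a separate question about what the CV means. It does not follow from the two-parameter rule and is not used here.

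Finally, this is not a detail left to the SAP: the protocol itself fixes both the success rule and the power figure.

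**Conclusion.** The point holds as a mismatch between two stated items. The 0.848 in section 8.6.8.1 is per parameter and per comparison at one-sided 0.00714, while section 8.6.7.1.3 requires both parameters. On the protocol's own inputs, joint power is about 0.75 to 0.80 for an AUC-Cmax correlation of 0.5 to 0.9, a shortfall of about 4 to 10 points.

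This rests on three assumptions: that correlation range, which the protocol does not give; equal effect and equal CV for both parameters; and the first Holm step. A lower CV or larger effect on one parameter narrows the gap, and rejection of several other comparisons can close or reverse it. The mismatch does not by itself show that the trial is too small.

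**What to change.** In section 8.6.8.1, state that 0.848 is the power per parameter and per comparison at one-sided 0.00714. Add the joint power for the rule that both must be significant over an assumed AUC-Cmax correlation of 0.5 to 0.9 (about 0.75 to 0.80). Say that this assumes equal effect and CV for the two parameters and the first Holm step.

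Leave the sample size, the success rule and the analysis as they are. The cost is a sentence or two, a short calculation and a less favourable stated power.
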